## **14 Insurance**

The study is covered under the Sponsor's liability insurance policy. A certificate of insurance containing essential information about the insurance coverage can be provided to the study Sites upon request.

## **15 Publication Policy**

The Sponsor of this study, recognizing the seminal importance of this investigation, is committed to the unrestricted and widespread dissemination of all primary and secondary endpoint results and tertiary analyses. At the conclusion of the study, a multicenter abstract reporting the primary results may be prepared by the Principal Investigators (in collaboration with the Executive Committee, directors of the core laboratories, clinical events committee, and Primary Investigators from high enrolling sites) and presented at an annual scientific meeting (e.g., Transcatheter Cardiovascular Therapeutics, EuroPCR, the American Heart Association, or the American College of Cardiology). A multicenter publication may similarly be prepared for publication in a reputable scientific journal. The publication of the principal results from any single center experience within the trial is not allowed until both the preparation and publication of the multicenter results.

Following analysis and presentation of the primary endpoint results, active participation of all committee members, Investigators from high enrolling sites, and core laboratory personnel will be solicited for data analysis and abstract and manuscript preparation. Submission of all abstracts and publications regarding the primary endpoint and secondary endpoints from the study requires approval by the Principal Investigators after review by the Executive Committee.

2. STUDY SYNOPSIS

Protocol Number	VP-0730
Title	A Prospective, Open Label, Multi-center, Single Arm, Observational Study Designed to Evaluate the Safety and Device Procedural Success of the Scoreflex NC Scoring PTCA Catheter in Subjects with Stenotic Coronary Arteries during Percutaneous Coronary Intervention
Study Devices	Scoreflex NC Scoring PTCA catheter
Objective(s)	The objective of this study is to assess the acute safety and device procedural success of the Scoreflex NC scoring PTCA catheter in its intended use for the dilatation of coronary artery stenosis ($\geq 70\%$ diameter stenosis).
Design	Prospective, open label, multi-center, single arm, observational study
Study Population	Subjects with evidence of ischemia and clinically indicated for one- or two-vessel revascularization procedures by percutaneous coronary intervention
Sample Size	Two-hundred (200) subjects will be enrolled at up to 15 U.S. sites
Inclusion Criteria	
General Inclusion Criteria
 
 1. Subject is ≥ 18 years of age 2. Subject or a legally authorized representative must provide written informed consent prior to any study related procedures 3. Subject must agree not to participate in any other clinical study during hospitalization for the index procedure that would interfere with the endpoints of this study 4. Subjects must have a single or double vessel coronary artery disease and clinical evidence of ischemic heart disease, such as CAD, stable / unstable angina or silent ischemia
Angiographic Inclusion Criteria	
 5. Subject must have de novo or restenotic lesion(s) in native coronary arteries, including in-stent restenosis suitable for percutaneous coronary intervention. 6. A maximum of two lesions, including at least one target lesion, in up to two coronary arteries. 7. Target lesion must have a reference vessel diameter (RVD) between 1.75 and 4.0 mm by visual estimation.

	
8. Target lesion(s) must have a diameter stenosis of $\geq 70\%$ by visual estimation and may include chronic total occlusions (CTO).
 
9. The non-target lesion must be located in different coronary artery from the Target lesion.
 
10. Treatment of non-target lesion, if any, must be completed prior to treatment of target lesion and must be deemed a clinical angiographic success as visually assessed by the physician


Exclusion Criteria
	
General Exclusion Criteria
 
 1. Subject with a known hypersensitivity or contraindication to aspirin, heparin, bivalirudin, anti-platelet medications, or sensitivity to contrast media which cannot be adequately premedicated 2. Subject with known diagnosis of STEMI or NSTEMI at index presentation or within 7 days of study screening 3. Subject with known pregnancy or is nursing. Women of child-bearing potential should have a documented negative pregnancy test within 7 days before index procedure 4. Planned or actual target lesion treatment with an unapproved device, atherectomy, laser, cutting balloon or thrombectomy during the index procedure 5. A serum creatinine level > 2.0 mg/dl within 7 days prior to index procedure 6. Cerebrovascular accident (CVA) within the past 6 months 7. Active peptic ulcer or active gastrointestinal (GI) bleeding within the past 6 months 8. Subject has a known left ventricular ejection fraction (LVEF) $< 30\%$ (LVEF may be obtained at the time of the index procedure if the value is unknown, if necessary) 9. Target lesion located within an arterial or saphenous vein graft or graft anastomosis

Angiographic Exclusion Criteria
	
 10. More than two lesions requiring treatment. 11. Target lesion longer than 30 mm by visual estimation. 12. Extreme angulation (90° or greater) proximal to or within the target lesion. 13. Previous percutaneous intervention of lesions in a target vessel (including side branches) conducted within 9 months before the study procedure and located within 10 mm from the current target lesion. 14. Target lesion demonstrating severe dissection prior to planned deployment of the Scoreflex NC device 15. Unprotected left main coronary artery disease. (Greater than

	
50% diameter stenosis)
 
16. Coronary artery spasm of the target vessel in the absence of a significant stenosis.
 
17. Target lesion with angiographic presence of probable or definite thrombus.
 
18. Target lesion involves a bifurcation requiring treatment with more than one stent or pre-dilatation of a side branch >2.0 mm in diameter.
 
19. Non-target lesion to be treated during the index procedure meets any of the following criteria:
 
 • Located within a bypass graft (venous or arterial) • Left main location • Chronic total occlusion • Involves a bifurcation (e.g., bifurcations requiring treatment with more than 1 stent) • Treatment not deemed a clinical angiographic success
Subject screening and enrollment process	A subject is considered enrolled in the study following provision of informed consent and upon insertion of the investigational device into a guide catheter.
Study Duration/Follow-Up Period	Subjects will be followed through hospital discharge.
Primary Effectiveness Endpoint	
Device procedural success consisting of the following:
 
 • Successful delivery, inflation, deflation, and withdrawal of the study balloon • No evidence of vessel perforation, flow limiting dissection (grade C or higher) or reduction in TIMI flow from baseline as related to the Scoreflex NC study balloon • Final TIMI flow grade of 3 at the conclusion of the PCI procedure
Secondary Endpoints	
Angiographic Procedural efficacy:
 
 • Final diameter stenosis \leq 50% in at least one of the Scoreflex NC attempted lesions following completion of the interventional procedure, including adjunctive stenting 
The following clinical endpoints will be measured through hospital discharge:
 
 • In-hospital Major Adverse Cardiac Events (MACE), a composite of: 
 ○ All death (cardiac and non-cardiac) ○ Myocardial infarction (MI)

	
 ○ Target Lesion Revascularization (TLR), clinically indicated ○ In-hospital stent thrombosis (ST) within the target vessel ○ Clinically significant arrhythmias (requiring intervention)

Statistical Considerations
	
A sample size of two-hundred (200) subjects has been chosen in order to characterize the performance of the device.
 
Statistical analyses will be performed for the primary, secondary endpoints, and additional analyses based on analysis populations that are defined below.
 
Primary Analysis Set:
 
The primary analysis set is the Intent-to-Treat (ITT) population. The ITT population includes all consented and enrolled subjects.
 
Secondary Analysis Set:
 
The secondary analysis set is the Per-Protocol (PP) population. The PP population is defined as all enrolled subjects who received a Scoreflex NC device with availability of data of the primary endpoint and without any major protocol violations including the violation of inclusion or exclusion criteria

Lesions
	
A maximum of two lesions, including at least one target lesion, may be treated during the index procedure.
 
Non-target lesion should be treated first and deemed a clinical angiographic success by visual assessment prior to treatment of the target lesion.
 
The lesion identified as the target lesion is intended to be treated during the index procedure with a Scoreflex NC study device.
 
Non-Target Lesion
 
 • A maximum of one non-target lesion (in addition to one target lesion in a target vessel) may be treated in a non-target vessel with a commercial treatment during the index procedure and must occur prior to treatment of target lesion.

	
• Treatment of non-target lesion must be deemed a clinical angiographic success for subjects to be eligible for enrollment into the study.• Target and non-target lesions must be located in different coronary arteries. 
Target Lesion
 
• Lesion that is to be treated with the Scoreflex NC study device during the index procedure.• Target lesions (maximum of 2) may be located in the same or different coronary arteries.• Target lesion composed of multiple focal lesions that can be covered with one stent will be considered as a single lesion. 
Note: A separate Scoreflex NC study device must be used for treatment of each target lesion.

--	--

TABLE OF CONTENTS

Section	Page
1. SIGNATURE PAGE	ii
2. STUDY SYNOPSIS	i
3. LIST OF ABBREVIATIONS AND DEFINITIONS OF TERMS	7
4. INTRODUCTION	8
5. STUDY OBJECTIVES	9
6. INVESTIGATIONAL PLAN	10

3. LIST OF ABBREVIATIONS AND DEFINITIONS OF TERMS

Abbreviation	Definition
AE	Adverse Event
CRF	Case Report Form
CSR	Clinical Study Report
CTO	Chronic Total Occlusions
CVA	Cerebrovascular Accident
EDC	Electronic Data Capture
GCP	Good Clinical Practice
GI	Gastrointestinal
ICH	International Conference on Harmonization
IRB	Institutional Review Board
ISO	International Organization for Standardization
ITT	Intent to Treat
LVEF	Left Ventricular Ejection Fraction
MACE	Major Adverse Cardiac Event
MI	Myocardial infarction
MLD	Minimum Lumen Diameter
PCI	Percutaneous Coronary Intervention
PP	Per Protocol
PTCA	Percutaneous Transluminal Coronary Angioplasty
QCA	Quantitative Coronary Angiography
RVD	Reference Vessel Diameter
SAP	Statistical Analysis Plan
SAS	Statistical Analysis System
ST	Stent thrombosis
US	United States

4. INTRODUCTION

The Scoreflex NC Scoring PTCA Catheter is a coronary dilatation catheter designed with a short rapid-exchange tip distal to the dilation balloon and an external integral wire on the outside of the balloon, such that the guide wire and the integral wire act as scoring elements external to the balloon when the balloon is inflated. The presence of the external scoring elements outside the angioplasty balloon create a focal stress pattern which allows for opening of lesions at lower pressures using a concept of Focused Force Angioplasty.

The target study population is subjects with evidence of ischemia and clinically indicated for one- or two-vessel revascularization procedures by percutaneous coronary intervention.

The statistical analysis plan (SAP) is intended to prospectively (*a priori*) outline the analyses and presentations of data that will form the basis for conclusions to be reached to answer the study objectives outlined in the protocol, and to explain in detail how the data will be handled and analyzed, adhering to commonly accepted standards and practices of biostatistical analysis in clinical trials. Results obtained from the analyses outlined in this document will be the basis for the clinical study report (CSR) for this study. This plan is based on Revision 1 of the study protocol, dated 30 November 2018.

5. STUDY OBJECTIVES

As stated in the protocol, the objective of this study is to assess the acute safety and device procedural success of the Scoreflex NC scoring PTCA catheter in its intended use for the dilatation of coronary artery stenosis ($\geq 70\%$ diameter stenosis).

6. INVESTIGATIONAL PLAN

6.1. Overall Study Design and Plan

This is a prospective, open label, multi-center, single arm, observational study designed to evaluate the acute safety and device procedural success of the Scoreflex NC scoring PTCA catheter in subjects with stenotic coronary arteries during percutaneous coronary intervention.

Two-hundred (200) subjects are treated at up to 15 U.S. sites with the Scoreflex NC catheter during their index procedure. All subjects are screened according to the protocol inclusion and exclusion criteria and are followed through hospital discharge.

6.1.1. Choice of Control Groups

There is no control group in this study because this is a single-arm study.

6.1.2. Method of Assigning Subjects to Treatment Groups

Assignment to treatment groups is not applicable because this is a single-arm study. All subjects will receive the Scoreflex NC Scoring PTCA catheter.

6.1.3. Blinding

The study is an open-label observational study. Therefore, there is no blinding procedure applied in this study.

6.2. Description of study hypotheses and endpoints

There are no hypotheses defined in this study.

6.2.1. Primary Safety and Efficacy Endpoint

The primary endpoint is a successful procedure based on the following composite components on a per-patient level:

- Successful delivery, inflation, deflation, and withdrawal of the study balloon
- No evidence of vessel perforation, flow limiting dissection (grade C or higher) or reduction in TIMI flow from baseline as related to the Scoreflex NC study balloon
- Final TIMI flow grade of 3 at the conclusion of the PCI Procedure

A patient's procedure is considered a success if all three components are achieved.

Each component of the primary endpoint measures will be reported as individual components as well..

6.2.2. Secondary Endpoints

The secondary endpoints consist of angiographic procedural efficacy, clinical, and peri-procedural endpoints.

The secondary angiographic procedural efficacy endpoint is measured and defined as follow:

- Final diameter stenosis $\leq 50\%$ in at least one of the Scoreflex NC attempted lesions following completion of the interventional procedure, including adjunctive stenting

The secondary clinical endpoints which are measured through hospital discharge are as follows:

- In-hospital Major Adverse Cardiac Events (MACE), a composite of the following:
 - All death (cardiac and non-cardiac)
 - Myocardial infarction (MI)
 - Clinically indicated Target Lesion Revascularization (TLR)
- In-hospital stent thrombosis (ST) within the target vessel
- Clinically significant arrhythmias (requiring intervention)

The secondary peri-procedural endpoints are measured through hospital discharge and defined as follows:

- Occurrence of Scoreflex NC study balloon rupture
- Improvement in Minimum Lumen Diameter (MLD) following use of Scoreflex NC coronary dilatation catheters (measured by QCA)

Both MI and ST are to be determined by the Academic Research Consortium (ARC) classification criteria. MI will be classified into various types including the 99th percentile upper reference limit (URL) decision limits for biomarkers employed.

Myocardial Infarction will be defined as:

- Q-Wave MI: Development of new (i.e., not present on the subject's ECG before allocation) pathological Q-waves in 2 or more leads lasting 0.04 seconds with post-procedure CK-MB levels elevated above normal.
- Non-Q-Wave MI: Elevation of post-procedure CK-MB levels to >3.0 times ULN without new Q-waves.

For subjects undergoing bypass surgery, a peri-operative MI will be defined as follows:

a) Total CK-MB $>5\times$ ULN.

or

b) Presence of new pathologic Q-waves as defined above.

7. DATA QUALITY ASSURANCE AND COMPUTING ENVIRONMENT

Case report forms (CRFs) for data collection were created on an Electronic Data Capture (EDC) system specifically for this study and were used to record data. The forms were completed by the study site personnel, overseen and approved by the Investigators. All procedures for the handling and analysis of data were conducted using Good Clinical Practices (GCP) meeting the International Organization for Standardization (ISO) 14155 and the International Conference on Harmonization (ICH) guidelines and the US Food and Drug Administration regulations for the handling and analysis of data for Clinical Investigations.

All statistical analyses will be performed using the Statistical Analysis System (SAS) Software package, Version 9.4 or higher (SAS Institute, Cary, NC).

8. SUBJECT POPULATIONS

The following analysis populations are defined for the purpose of analysis: an Intent to Treat (ITT) population, and a Per Protocol (PP) population. The primary endpoint analysis and all other secondary endpoint analyses will be carried out on both ITT and PP populations unless otherwise stated in the final clinical summary report. The analyses of adverse events will be carried out on the ITT population.

8.1. Analysis Populations

The primary analysis set is the ITT population. The ITT population includes all consented and enrolled subjects.

The PP population is defined as all enrolled subjects who received a Scoreflex NC device with availability of data of the primary endpoint and without any major protocol violations including the violation of inclusion or exclusion criteria as shown below. The PP population will be used for confirmatory analysis of efficacy endpoints. Categories of Major protocol deviations are defined in Section 8.2.

The following are inclusion and exclusion criteria.

Inclusion Criteria

1. Subject is ≥ 18 years of age
2. Subject or a legally authorized representative must provide written informed consent prior to any study related procedures.
3. Subject must agree not to participate in any other clinical study during hospitalization for the index procedure that would interfere with the endpoints of this study.
4. Subjects must have a single or double vessel coronary artery disease and clinical evidence of ischemic heart disease, such as CAD, stable / unstable angina or silent ischemia

Angiographic Inclusion Criteria

5. Subject must have de novo or restenotic lesion(s) in native coronary arteries, including in-stent restenosis suitable for percutaneous coronary intervention.
6. A maximum of two lesions, including at least one target lesion, in up to two coronary arteries.
7. Target lesion must have a reference vessel diameter (RVD) between 1.75 and 4.0 mm by visual estimation.
8. Target lesion(s) must have a diameter stenosis of $\geq 70\%$ by visual estimation and may include chronic total occlusions (CTO).

Exclusion Criteria

General Exclusion Criteria

1. Subject with a known hypersensitivity or contraindication to aspirin, heparin, bivalirudin, anti-platelet medications, or sensitivity to contrast media which cannot be adequately premedicated

2. Subject with known diagnosis of STEMI or NSTEMI at index presentation or within 7 days of study screening
3. Subject with known pregnancy or is nursing. Women of child-bearing potential should have a documented negative pregnancy test within 7 days before index procedure
4. Planned or actual target lesion treatment with an unapproved device, atherectomy, laser, cutting balloon or thrombectomy during the index procedure
5. A serum creatinine level > 2.0 mg/dl within 7 days prior to index procedure
6. Cerebrovascular accident (CVA) within the past 6 months
7. Active peptic ulcer or active gastrointestinal (GI) bleeding within the past 6 months
8. Subject has a known left ventricular ejection fraction (LVEF) <30% (LVEF may be obtained at the time of the index procedure if the value is unknown, if necessary).
9. Target lesion located within an arterial or saphenous vein graft or graft anastomosis

Angiographic Exclusion Criteria

10. More than two lesions requiring treatment.
11. Target lesion longer than 30 mm by visual estimation.
12. Extreme angulation (90° or greater) proximal to or within the target lesion.
13. Previous percutaneous intervention of lesions in a target vessel (including side branches) conducted within 9 months before the study procedure and located within 10 mm from the current target lesion.
14. Target lesion demonstrating severe dissection prior to planned deployment of the Scoreflex NC device
15. Unprotected left main coronary artery disease. (Greater than 50% diameter stenosis)
16. Coronary artery spasm of the target vessel in the absence of a significant stenosis.
17. Target lesion with angiographic presence of probable or definite thrombus.
18. Target lesion involves a bifurcation requiring treatment with more than one stent or pre-dilatation of a side branch >2.0 mm in diameter.
19. Non-target lesion to be treated during the index procedure meets any of the following criteria:
 - Located within a bypass graft (venous or arterial)
 - Left main location
 - Chronic total occlusion
 - Involves a bifurcation (e.g., bifurcations requiring treatment with more than 1 stent)
 - Treatment not deemed a clinical angiographic success

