#### **4.1 Selection and Withdrawal of Subjects**

Once the subjects have signed the Institutional Review Board (IRB) approved study informed consent form (ICF) and research authorization forms (RA/HIPAA) and have met all general inclusion and exclusion criteria, the subjects will be considered eligible to be enrolled in the study to receive treatment with the Scoreflex NC dilatation catheter. A subject is considered enrolled in the study upon insertion of the investigational device into a guide catheter. Upon enrollment, a subject identification number will be assigned to each subject in a consecutive manner within each clinical site.

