### 5.3.5 Completion of Index Procedure

The completion of the Index Procedure is defined as the time the guide catheter is removed, post final angiography. The following information should be collected:

- Document procedural information, including non-target lesion (if applicable), target lesion of lesions with use of the Scoreflex NC study balloon, stent (if applicable) and post-dilatation (if applicable) on the appropriate CRFs.
- Record cardiac medications
- Record antithrombotic and antiplatelet medications.
- If an AE should occur, Complete AE assessment and source document collection
- Record any device deficiencies that might have occurred before or during the procedure as described in Section 8.

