## **12 Ethics**

All subjects must provide written informed consent in accordance with the Site's IRB, using an IRB-approved informed consent form. The final eligibility for the trial will be the final pre-intervention angiographic qualification.

Study-specific procedures must not be performed until a signed informed consent has been obtained. The Investigator/designee, who has been trained on the protocol, will explain the nature and scope of the study, potential risks and benefits of participation, and answer questions from the patient.

All subjects are to be fully informed and study conduct must be in accordance with the World Medical Association Declaration of Helsinki: Ethical Considerations for Medical Research Involving Human Subjects.

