8.2. Protocol Deviations

Protocol deviations will be categorized as Major and Minor.

Major deviations include those that involve the informed consent process, and the inclusion/exclusion criteria of the study.

Minor deviations include all other noted deviations, i.e. Missed Assessment, Assessment not done in the required timeframe, and other.

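### Read literally, exclusion 4 can drop subjects from the per-protocol set after the study device has failed, and the SAP does not say whether that reading applies

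*SAP*

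**What the plan says.** The point turns on how several sections combine.

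- **Enrollment.** Protocol 4.1: "A subject is considered enrolled in the study upon insertion of the investigational device into a guide catheter". The subject is therefore in the study before anyone knows whether the balloon can be delivered.
- **Exclusion 4**, in the SAP 8.1 list that defines PP: "Planned or actual target lesion treatment with an unapproved device, atherectomy, laser, cutting balloon or thrombectomy during the index procedure".
- **End of the procedure.** Protocol 5.3.5: "The completion of the Index Procedure is defined as the time the guide catheter is removed, post final angiography".
- **Deviation class.** SAP 8.2: "Major deviations include those that involve the informed consent process, and the inclusion/exclusion criteria of the study". SAP 8.1 takes subjects with major violations out of PP. It also limits PP to subjects who received a Scoreflex NC device, without saying what counts as receiving it.
- **Eligibility timing.** Protocol section 12 (Ethics): "The final eligibility for the trial will be the final pre-intervention angiographic qualification".
- **Primary endpoint.** SAP 6.2.1: "A patient's procedure is considered a success if all three components are achieved". Component 1 is delivery, inflation, deflation and withdrawal of the balloon. Component 2 is freedom from balloon-related perforation, flow-limiting dissection or loss of TIMI flow. Component 3 is final TIMI 3 flow.
- **Role of PP.** SAP 8.1: "The PP population will be used for confirmatory analysis of efficacy endpoints". ITT is the primary analysis set.

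**The concern.** A per-protocol set should not lose subjects because the device under study did not work. If the balloon cannot be delivered, or causes a dissection, and the operator then uses one of the devices named in exclusion 4, the literal rule makes that subject a major violator. The subject counts as a failure in ITT and is absent from PP. The reason for leaving PP would then be a consequence of the outcome that the endpoint measures.

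The documents also allow the opposite reading, under which later device use is not an eligibility violation and the subject stays. Two programmers working from the same SAP could build different PP sets. Tables 10.2.1, 10.2.2 and 11.2 would be affected, together with the confirmatory role that SAP 8.1 gives to PP.

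**Working it through.** **Step 1: the literal chain.** The subject is enrolled at guide-catheter insertion. Exclusion 4 covers actual as well as planned use, at any time in the index procedure. That procedure runs to guide-catheter removal, so it includes whatever follows a failed attempt. Any deviation from the inclusion or exclusion criteria is major, with no exception for events after enrollment, and a major violation removes the subject from PP.

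**Step 2: a comparison within the same list.** Exclusion 14 carries its own time limit: "Target lesion demonstrating severe dissection prior to planned deployment of the Scoreflex NC device". Exclusion 4 has none.

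**Step 3: the competing reading.** Protocol section 12 places final eligibility before the intervention, and Protocol 4.1 and 5.3.1 require the general criteria to be met before a subject is eligible to be enrolled. On that view, use after the attempt is at most one of the remaining deviations, which SAP 8.2 classes as minor, and the subject stays in PP. No section says which reading governs PP.

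**Step 4: direction.** Let F be the failures among 200 subjects, f the failures removed from PP and s the successes removed.

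PP rate = (200 − F − s) / (200 − f − s)

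This exceeds the ITT rate, (200 − F)/200, if and only if f/(f + s) > F/200. If only failures are removed (s = 0, f > 0), the PP rate is always higher.

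**Step 5: scale.** The plan has no figure to reproduce: 200 subjects were chosen without a hypothesis (SAP 9.1), and the documents give no failure counts. F and f below are assumptions, with s = 0. Intervals are two-sided exact (Clopper-Pearson) 95%, matching the exact intervals in SAP 9.2.1.

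| F assumed | ITT rate | f removed | PP rate |
|---|---|---|---|
| 5 | 195/200 = 97.5% (94.3 to 99.2) | 2 | 195/198 = 98.5% (95.6 to 99.7) |
| 10 | 190/200 = 95.0% (91.0 to 97.6) | 1 | 190/199 = 95.5% (91.6 to 97.9) |
| 10 | as above | 2 | 190/198 = 96.0% (92.2 to 98.2) |
| 10 | as above | 5 | 190/195 = 97.4% (94.1 to 99.2) |
| 20 | 180/200 = 90.0% (85.0 to 93.8) | 10 | 180/190 = 94.7% (90.5 to 97.4) |

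With F = 10 the rise is 0.5 points when one failure is removed and 2.4 points when five are. Removing only successes moves the rate the other way: with F = 10, f = 0 and s = 10 it is 180/190 = 94.7%, or 0.3 points below ITT. The documents set no limit on s, so these figures illustrate scale and do not bound the effect.

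**The case against.** **Little depends on PP.** ITT is primary, PP is the secondary set, and no hypothesis is tested. Tables 10.1.1 and 10.2.1 set ITT beside PP, and the disposition table and Table 9 count violators and deviations. This stands, and it limits the weight of the point. None of that output, however, is specified to show whether a listed device followed a failed attempt.

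**The conflict with Protocol section 12 is indirect.** A reader might infer a flat contradiction. The documents do not support that: it is one sentence in the Ethics section, it speaks of angiographic qualification, and it does not mention PP, while exclusion 4 sits among the clinical criteria.

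**Already a failure is not certain in every case.** The endpoint does not say whether delivery is judged on the first attempt or on any attempt. If a first attempt fails, a listed device is used and Scoreflex NC is then delivered, the status of component 1 is open. The upward direction therefore holds generally, not without exception.

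**Exclusion 4 may not be the only route out.** A failed-delivery subject might also be judged not to have received the device. The number lost through exclusion 4 alone cannot be known, and a repair that leaves this term undefined would be incomplete.

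**An extreme PP rate.** A reader might infer that PP could reach 100%. Arithmetically it could, but only if every failure were followed by a listed device, and nothing in the documents supports that. Failures managed only with stents or plain balloons are not named in exclusion 4 and stay in PP.

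**Conclusion.** The point holds as a gap in the definition of the PP set. Read literally, SAP 8.1 and 8.2 remove an enrolled subject for listed-device use at any time in the index procedure, including after an unsuccessful Scoreflex NC attempt. This can take device failures out of PP and raise its success rate, and the documents do not say whether that reading applies. The direction assumes that the removed subjects had already failed component 1 or 2 and that an earlier failed attempt counts as a failure.

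The size is unknown. On the assumed 10 failures in 200, the rise is 0.5 points for one removal and 2.4 points for five.

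A reader might infer that the primary result is compromised or that the plan is built to flatter the device. The documents support neither: the ITT analysis keeps every enrolled subject, and a competing reading would keep these subjects in PP as well. It is worth correcting because the SAP gives PP a confirmatory role and the correction is cheap.

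**What to change.** Change the SAP analysis-set definition only, leaving eligibility and clinical management as they are.

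1. In 8.1 and 8.2, reconcile exclusion 4 with Protocol section 12 by a rule based on timing alone, applied to every subject whatever the endpoint status. For PP membership, only listed-device use planned or carried out before the first Scoreflex NC attempt counts as a violation of exclusion 4. Use that first arises after that attempt does not remove the subject, whose endpoint is scored as observed. A rule that kept failures but allowed successes with the same treatment to be dropped would itself depend on outcome and should be avoided.
2. Define receipt of the device so that an attempted but failed delivery counts, for example insertion into the guide catheter, which matches the enrollment definition.
3. Call PP supportive instead of confirmatory.
4. Report the number and endpoint status of subjects with listed-device use after the attempt. Footnote that their final TIMI flow and stenosis may reflect the other device.
5. Document the change under SAP section 12, and set the rule without reference to endpoint counts. The study is open label and SAP section 7 already describes form completion in the past tense.

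**Cost.** This needs a few lines of wording, one count and a footnote. The PP rate may be slightly less favourable, and some PP final results will not be attributable to Scoreflex NC alone. The order of device use must be confirmed from procedure records, because Protocol 5.3.5 names the study balloon, stent and post-dilatation but not the devices in exclusion 4.
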